7.2 Flowchart

	Screening	Baseline Endoscopy	Flare	Week 44
Study information				
provided and				
information sheet	Х			
mailed.	^			
Inclusion/exclusion				
criteria reviewed.				
Patient information				
and informed		Х		
consent completed.				
Collection of				
demographic and		Х		
baseline clinical data				
Collection of clinical				
activity score	Х	Х	Х	Х
(SCCAI)				
Routine endoscopic				
assessment and		х	Х	х
collection of tissue		Λ	Λ	~
for routine histology				
Collection of				
research blood and		Х	Х	Х
tissue samples				
Collection of clinical				
data, routine blood		х	Х	х
tests and faecal		~		~
calprotectin				

8 Subject selection

Adult patients with ulcerative colitis on tofacitinib 10mg BD who are having their tofacitinib reduced to the maintenance dosing of 5mg BD in view of adequate response will be eligible for recruitment. The patients will be identified from Guy's and St Thomas' cohort of ulcerative colitis patients receiving tofacitinib. We expect there will be approximately 50 patients per year eligible for this trial. Given that the only difference to usual care is the additional blood and tissue samples collected at baseline and flare or week 44, we expect most patients would agree to this study.

8.1 Subject inclusion criteria

- 1. Aged 18 years or over, either male or female
- 2. A history of ulcerative colitis, as defined by standard clinical criteria
- 3. Patients who are having their tofacitinib dose reduced from 10mg BD to 5mg BD in view of adequate response, as decided by their treating clinical team, and are undergoing routine endoscopy.

4. Sufficient English language skills to understand the patient information sheet and consent form.

8.2 Subject exclusion criteria (with justification if necessary – for example consider contra-indications to trial treatments, incompatible concurrent treatments, recent involvement in other research)

- 1. Patients undergoing dose reduction for reasons other than adequate response to 10mg bd (ie. active infection or VTE risk).
- 2. Patients being dose reduced without undergoing endoscopy

9 Study procedures

9.1 Subject recruitment

- Patients who have clinically responded to 10mg BD tofacitinib, are approaching their routine endoscopy and who are being considered for dose reduction by their treating team, will be identified.
- Potential participants will most likely be identified from our database of patients currently on tofacitinib but could be identified by any member of the multidisciplinary direct care team, including registrars, clinical research fellows, consultants, as well as clinical nurse specialists, IBD research nurses or pharmacists. Potential participants could be identified at outpatient clinics, or during our weekly multidisciplinary meeting (Virtual biologics and immunosuppressant clinic).
- Prior to their routine endoscopy, potential participants will be approached via telephone or during a clinic consultation. An information sheet and consent form will be given to them or sent by post or via e-mail. Patients will be allowed at least 48 hours to decide if they wish to consent to participate, although patients can be consent earlier than 48 hours if they wish. Consent may also be obtained on the day of endoscopy from one of the study's medical practitioners.
- There will be no payment to participants for their involvement in the study

9.2 Screening Procedures

- Screening phone call:
 - o Inclusion/exclusion criteria reviewed
 - Information provided on the study, and information sheet and informed consent form sent to patient in the mail or via e-mail.

9.3 Schedule of Assessment for each visit

Patients in whom the treating team is planning to reduce their Tofacitinib from 10mg BD to 5mg will be referred for consideration of inclusion in the study.

- 1. Screening phone call
 - a. Information regarding the study provided
 - b. Inclusion/exclusion criteria reviewed
 - c. Patient information sheet, and consent form sent to patient in the mail or via e-mail.
- 2. Routine baseline endoscopy
 - a. Informed consent gained and form signed, prior to the endoscopy.
 - b. Baseline clinical data collected
 - c. Endoscopy performed and biopsies taken from rectum and sigmoid, to be sent for:

Guy's and St Thomas' Miss

NHS Foundation Trust

- i. Histological assessment of disease activity (Nancy Histological Index)
- ii. Genetic analysis
- iii. Future exploratory analysis
- d. Blood collection, to be sent for:
 - i. Routine clinical bloods (FBC, CRP, LFTs, U&E)
 - ii. STAT activation in peripheral blood mononuclear cells
 - iii. Cytokine expression in peripheral T cells
- e. Faecal calprotectin submitted
- 3. Flare (SCCAI \geq 5)
 - a. Should a clinical flare occur, patients will be encouraged to contact our IBD advice line as per current standard of care.
 - b. Routine and study blood tests, stool, and endoscopic tests will be initiated, as per standard of care, and the decision on how to manage the clinical flare will be taken by the treating team. Additional study biopsies will be taken at the time of the endoscopy.
- 4. Routine clinical visits
 - a. These will occur as per the treating team's discretion, with testing performed accordingly.
- 5. Week 44
 - a. In patients who remain on tofacitinib at week 44, routine clinical assessment will occur.
 - b. Tests performed will be
 - i. Routine endoscopy and biopsies, sent for:
 - 1. Histological assessment of disease activity (Nancy index) (part of routine care)
 - ii. Study biopsies, sent for:
 - 1. Genetic analysis
 - 2. Future exploratory analysis
 - iii. Routine blood collection, to be sent for:
 - 1. Routine clinical bloods (FBC, CRP, LFTs, U&E)
 - 2. Study blood tests will also be taken at this time point
 - iv. Routine faecal calprotectin

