	dose commencing on maintenance tofacitinib therapy.
Primary objective	To identify biochemical and genetic markers predictive of
	ulcerative colitis flare
Secondary objective (s)	To identify clinical and disease characteristics predictive
	of ulcerative colitis flare
Number of Subjects/Patients	50 patients
Trial Design	Prospective observational study
Endpoints	1. Flare requiring drug discontinuation, surgery
	(colectomy) or addition of new therapy for ulcerative
	colitis.
	2. Endoscopic activity at week 44 endoscopy
Main Inclusion Criteria	Ulcerative colitis patients commencing tofacitinib
	maintenance dosing, undergoing endoscopy as part of
	their routine clinical care.
Statistical Methodology and Analysis	Receiver operator curves will be generated to determine
	optimal cut-offs for continues variables, predictive of
	disease flare.
	Kaplan-Meier curves will be generated to allow
	comparisons of subdivisions of patients based on genetic
	and biochemical variables, using determined cut-offs.
	Univariate and Multivariate analyses will be performed on
	clinical, biochemical and genetic variables to establish
	predictors of disease flare.

5 Introduction

Tofacitinib has been shown in large-scale randomised clinical trials to be an effective treatment for patients with moderate to severe UC that is resistant to both conventional treatment and to biologic therapy¹. In the few months it has been available in the UK, our unit has accrued some of the biggest experience in the country. Our initial experience and prospectively collected observational data suggest that the drug performs at least as well as clinical trial results would indicate.

Results from the OCTAVE clinical trial program led to the approval of an induction regimen of 10mg BD, with subsequent dose reduction in responders to 5mg BD after at least 8 weeks. This maintenance regimen was shown to maintain remission with greater efficacy than placebo¹. However, the clinical trial data further suggests that in patients who have previously failed anti-TNF therapy, the 10mg BD maintenance dose is superior to the 5mg BD dosing¹. Anecdotally, many clinicians are accordingly favouring continuing the 10mg bd dose in higher risk patients (biologic failures) for up to 52 weeks, rather than dropping to the maintenance dose at week 8.

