We have the opportunity to systematically collect tissue from patients with UC treated with tofacitinib, as such we will undertake to track the mucosal immune response by multiparametric flow-cytometry study on endoscopic biopsies of the 50 patients within the BRITE study. These biopsies will be excess to these required to undertake the agreed experiments as part of the original study proposal – hence this proposal is of added benefit and will not detract from the funded study. This will facilitate flow cytometric immune monitoring of the architecture of the mucosal immune system (T cells, B cells and the myeloid compartment) at the point of de-escalation. Patients will subsequently be followed to relapse or the end of the study, whichever comes first, and tissue resampled to investigate the longitudinal changes in immunophenotype in the context of response to therapy. Similar immune monitoring has proved crucial at defining immune signatures in SARS-CoV-2 infection (15). This study is complementary to the work being performed in the original BRITE proposal and will provide more information on the effect of the drug on immunophenotypes and identify immunological signatures of response and or relapse – allowing a precision approach to drug selection.

6 Trial objectives and purpose

This is an investigator-initiated study with an overarching objective to identify biochemical and genetic markers of patients more likely to flare after tofacitinib dose reduction. It is hoped that this will eventually allow us to target continued higher dosing of 10mg bd at those patients who are most likely to benefit from it and avoid its use in patients in whom it is potentially unnecessary. Thereby, it would enable using the drug in a safer, more effective and more economical manner.

Primary objective:

• To identify biochemical, histologic and genetic markers predictive of ulcerative colitis flare in patients on tofacitinib commencing on maintenance 5mg BD dosing.

Secondary objectives:

- To identify clinical characteristics predictive of ulcerative colitis flare in patients on tofacitinib commencing on maintenance 5mg BD dosing.
- To identify predictors of endoscopic activity at week 44

7 Study design & Flowchart

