7.1 Study Design

This is a prospective observational study. We will prospectively enroll a cohort of 50 UC patients who have achieved an adequate response to tofacitinib at a dose of 10mg bd and whose dose is being reduced to 5mg bd following a routine flexible sigmoidoscopy. Colonic

tissue and blood samples will be collected at study entry, and patients' disease course will be followed-up through routine care.

Week 44 has been chosen for the primary endpoint, as 44 weeks post dose de-escalation was used as the endpoint in OCTAVE Sustain.

Primary endpoint:

• Biomarkers, clinical markers and histological markers associated with ongoing treatment with 5mg bd in the absence of steroids at week 44.

Secondary Endpoints

• Biomarkers, clinical markers and histological markers associated with steroid free endoscopic remission at routine endoscopy at week 44

Biomarkers / outcome measures will include:

- Clinical status (SCCAI)
- CRP and faecal calprotectin (as part of routine care)
- Histological markers of disease activity (Nancy histological index) (as part of routine care)
- STAT activation in peripheral blood mononuclear cells
- Cytokine expression in peripheral T cells
- Gene signatures in colonic biopsies

Guy's and St Thomas' MHS

NHS Foundation Trust

Flow Diagram

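### Section 9.3 provides the week-44 endoscopy only for patients still on tofacitinib, so those who stopped have no reading for the secondary endoscopic endpoint, and other sections state no such condition.

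*Protocol*

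**What the plan says.** Section 7.1 plans 50 patients: "We will prospectively enroll a cohort of 50 UC patients who have achieved an adequate response to tofacitinib". Its secondary endpoint is "Biomarkers, clinical markers and histological markers associated with steroid free endoscopic remission at routine endoscopy at week 44". Section 6 gives the matching objective, "To identify predictors of endoscopic activity at week 44", and the synopsis lists "2. Endoscopic activity at week 44 endoscopy".

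The schedule in section 9.3, item 5, sets who is seen at that time: "In patients who remain on tofacitinib at week 44, routine clinical assessment will occur". The tests of that visit follow as sub-item b, beginning with "Routine endoscopy and biopsies, sent for". No tofacitinib dose is attached to the condition.

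Other sections differ. The flowchart in 7.2 marks endoscopy, histology and research samples at week 44 with no on-drug condition. Section 10 has the Nancy index scored at baseline and week 44, and section 13.1 lists the endoscopic Mayo score and Nancy index at week 44, also without it. In the immune-monitoring part of section 5, on the other hand, follow-up ends early for some: "Patients will subsequently be followed to relapse or the end of the study, whichever comes first".

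Nothing in 7.1 or 14.2 says how a patient who stopped tofacitinib is classed on the endoscopic endpoint.

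**The concern.** The secondary endpoint is read from a procedure that, under 9.3, is provided only to patients with a particular post-baseline outcome: still taking the drug. Drug discontinuation, colectomy and new therapy are the events in the synopsis's first endpoint, so the patients without a reading include many of those the study wants to predict.

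Section 5 says the markers are to inform the decision when dose reduction is being considered. A remission rate or marker association estimated only in patients still on tofacitinib 44 weeks later answers a different question. It overstates remission among all who reduced dose, and it may misstate how well a baseline marker separates good from poor outcomes.

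**Working it through.** The protocol gives no event rate, stopping rate, effect size or power (14.1 says no sample size calculation is possible), so there is no stated figure to reproduce. The only documented number used is N = 50. All rates below are assumptions.

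**Evaluable patients.** n = 50 × (1 − f), where f is the proportion off tofacitinib by week 44. For f = 10, 20, 30, 40 and 50%, n = 45, 40, 35, 30 and 25.

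**Remission rate.** If stoppers count as not in remission, remission among all starters = (1 − f) × remission among those still on drug. With 50% observed remission, this gives 0.7 × 50% = 35% at f = 30%, and 0.6 × 50% = 30% at f = 40%. Under that classification the direction is fixed whenever anyone stops.

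**Marker association.** Let a binary baseline marker split the cohort 25/25. In each marker group, f is the probability of stopping and q the probability of not being in steroid-free endoscopic remission given still on drug.

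- On-drug-only: p = q, with 25(1 − f) patients per group.
- All starters, stoppers as failures: p = f + (1 − f)q, with 25 per group.
- Odds ratio = [p_high/(1 − p_high)] / [p_low/(1 − p_low)].

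Example with f = 40% vs 10% and q = 50% vs 30%:

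- All starters: 0.40 + 0.60 × 0.50 = 0.70, and 0.10 + 0.90 × 0.30 = 0.37. OR = (0.70/0.30)/(0.37/0.63) = 3.97.
- On-drug-only: OR = (0.50/0.50)/(0.30/0.70) = 2.33, from 15 + 22.5 = 37.5 patients.
- Remission: (15 × 0.50 + 22.5 × 0.70)/37.5 = 62% on drug, and 23.25/50 = 46.5% of all starters.

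| f high / low | q high / low | on-drug n | on-drug OR | all-starter OR | remission: on drug / all |
|---|---|---|---|---|---|
| 40% / 10% | 50% / 30% | 37.5 | 2.33 | 3.97 | 62% / 46.5% |
| 50% / 10% | 30% / 30% | 35 | 1.00 | 3.16 | 70% / 49% |
| 40% / 20% | 40% / 30% | 35 | 1.56 | 2.26 | 65.7% / 46% |
| 20% / 20% | 50% / 30% | 40 | 2.33 | 1.91 | 60% / 48% |
| 30% / 20% | 70% / 30% | 37.5 | 5.44 | 4.79 | 51.3% / 38.5% |

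In the first three rows the marker clearly predicts stopping, and the on-drug odds ratio is the smaller one. In the second row the signal vanishes. In the last two rows stopping is unrelated or only weakly related to the marker, and the on-drug odds ratio is the larger one.

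**The case against.** **Section 9.3 is a visit schedule, not an analysis rule.** The protocol defines no analysis set, and a statistical analysis plan that is not shown could class stoppers as not in remission. That is fair, so a reader should not infer that the protocol excludes these patients from analysis. But who has a week-44 endoscopy is a data-collection rule, and the protocol's sections disagree on it. Recoding can rescue the binary endpoint; it cannot supply activity or Nancy scores that were never taken. A flare endoscopy does not fill the gap either: 13.1 records its score only where one was done, and it is not a week-44 reading.

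**Not all failures are lost.** One might infer that every patient who failed drops out. The condition in 9.3 is remaining on tofacitinib, at no stated dose, so patients who flared and stayed on the drug are still assessed.

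**The main question is answered elsewhere.** The primary endpoint is "Biomarkers, clinical markers and histological markers associated with ongoing treatment with 5mg bd in the absence of steroids at week 44". Stopping already counts as failure there, so that endpoint is untouched.

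**Attenuation is not certain.** In a simulation where one latent severity drives both stopping and endoscopic activity, with half of those remaining in remission, an odds ratio of 2.5 per SD falls to about 1.98 at 30% stopping and 1.83 at 40%. That model builds the attenuation in. When stopping and endoscopic activity have separate error terms, the on-drug odds ratio stays near 2.5. The all-starter odds ratio (30%/40% stopping) is then 1.92/1.82 if stopping is unrelated to the marker, and 2.77/2.85 if its odds ratio for stopping is 2. This objection stands: the two analyses answer different questions, and neither is always the stronger.

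**Conclusion.** The point holds for the secondary endoscopic endpoint only. Followed as written, 9.3 makes the evaluable set depend on a post-baseline outcome, and 7.2, section 10 and 13.1 are not consistent with it.

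Remission among those still on drug overstates remission among all who reduced dose by a factor of 1/(1 − f), provided stoppers count as failures. The effect on marker associations is possible distortion. Attenuation is likely if the markers predict stopping, as the study's relapse hypothesis suggests when relapse leads to discontinuation. A reader might infer that the predictors are necessarily weakened, or weakened by a known amount. The documents give no stopping or remission rates, so neither inference is supported. The point should be put right, but it does not threaten the primary endpoint.

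**What to change.** 1. Reconcile 9.3 item 5 with 7.2, section 10 and 13.1, so that the protocol says in one way whose week-44 endoscopic and histological data are recorded.
2. In 7.1 and 14.2, define the binary secondary endpoint over all patients who start the reduced dose. Count discontinuation for flare, colectomy or new ulcerative colitis therapy before week 44 as not in steroid-free endoscopic remission.
3. Report stops without flare and missing endoscopies in two ways: as failures and excluded.
4. Add to 13.1 the date and reason for every stop. Treatment changes are now listed only under Flare, and section 12.2 covers reasons for leaving the study, not for stopping the drug.
5. Label any analysis of only those still on tofacitinib, including endoscopic activity scores, as conditional and descriptive.

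The binary definition costs some wording, one derived variable and a small addition to data collection; it needs no extra endoscopy. The drawbacks are a lower reported remission rate, overlap with the primary endpoint, and possible dilution of a marker related only to endoscopic activity (2.33 against 1.91 in the fourth row of the table).

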9.4 Follow up Procedures

See 9.5

9.5 Radiology Assessments

There are no planned radiology assessments as part of this study. While they may occur at the treating team's decision as part of the care of the patient, they will not be associated with this study.

9.6 End of Study Definition

The end of the trial will be deemed as date of final database lock and completion of analysis of laboratory samples collected from participants.

NHS Foundation Trust

10 Laboratories

Routine tests including blood tests (FBC, CRP, U&E, LFTs), and faecal calprotectin, will be performed as per standard of care at baseline, week 44, and at the treating team's discretion.

The Nancy Histological Index will be used to score histological disease activity, as per standard of care, at baseline and week 44.

Study specific tests of STAT activation, peripheral T cell cytokine expression, and genetic signature exploration will occur at baseline and flare or week 44.

10.1 Central/Local Laboratories

Routine blood and histological tests will be performed in the ViaPath lab at Guy's and St Thomas' hospitals. Faecal calprotectin will be performed at King's College Hospital. The STAT activation, cytokine expression and gene expression studies on blood and biopsy samples collected will be conducted in [name] and [name] labs in the Dept of Immunobiology, SIMS, [name], Guy's Hospital, KCL.

10.2 Sample Collection/Labelling/Logging

Biopsy samples will be taken by the endoscopist at the time of flexible sigmoidoscopy. Participants will have been recruited to the study prior to the procedure taking place and as part of that consent process will have had the chance to consider whether donating biopsy samples is acceptable to them. They will also be consented separately by the endoscopy team for the flexible-sigmoidoscopy procedure and biopsy sample acquisition (to be used as part of standard care, rather than research).

Samples will be taken from the rectum and sigmoid. They will be treated, transported and stored in accordance with HTA regulations. The histology specimens will be stored as per standard of care at GSTT. Biopsy samples for genetic analysis will be stored frozen in a laboratory in the Dept. of Immunobiology, SIMS, [name], Guy's Hospital, KCL. The custodians will be and [name] and [name].

Baseline blood tests will be collected by a practitioner qualified in this technique. Samples will be treated, transported and stored in accordance with HTA regulations in the Dept of Immunobiology, SIMS, [name], Guy's Hospital, KCL. The custodians will be [name] and [name].

All routine samples will be labelled at the point of collection as per hospital standards. Study samples will be labelled with patients' study number only. A record of all samples will be made at the point of collection and upon arrival at the laboratory.

None of these samples will be stored beyond the end of the study.

10.3 Sample Analysis Procedures

Standard lab processes will occur for the analysis of routine blood, faecal and histological tests.

STAT activation in peripheral T cells will be assessed by phospho-flow FACS analysis of PBMC using anti-phospho-tyrosine-STAT and anti-CD4, anti-CD3 and CD4 T-effector subset specific antibodies, according to standard protocols routinely used in our laboratory¹⁶. If

Guy's and St Thomas' MHS

NHS Foundation Trust

required, T cells maybe purified using magnetic bead isolation, prior to phospho-flow analysis. To confirm the results from the phospho-flow analysis and complement these studies, western blot analysis will be performed on a limited number of T cell samples to detect and quantify phosphorylated and total STAT protein levels. These are well established standard methods for detecting STAT activation, routinely in use in our laboratory.

We will evaluate cytokine expression in peripheral CD4 T cells following PMA/ionomycin stimulation for 4hrs, in the presence of GolgiStop (to prevent cytokine secretion), followed by intracellular cytokine staining and FACS analysis to detect specific cytokine expression. The supernatants from these cultures will be harvested and assessed for secreted cytokine expression using IL17, IFN γ and IL9-specific ELISA assays. Additionally, we will perform a multiplex cytokine array using the Th1/Th2/Th9/Th17/Th22/Treg ProcartaPlex Human Cytokine Array (Thermo Fisher Scientific) of patient plasma (frozen at -80C, upon isolation) to complement the FACS studies above. These are standard methods for detecting cytokine expression, routinely in use in our laboratory.

For genetic studies, RNA will be prepared using Qiaprep microRNA kit, then quantified on a Qubit instrument and 2ug RNA will be sent for library preparation and RNA-sequencing using commercial genomic services at Novogene. Briefly, mRNA is purified from total RNA using poly-T oligo-attached magnetic beads, then isolated mRNA is fragmented, reverse transcribed and stranded libraries will be prepared and sequenced using the Illumina platform to generate at least 20M reads per sample. Bioinformatic analysis of the RNA sequencing data will be carried out at Novogene as part of the service package and will provide comprehensive gene expression analysis. Unsupervised and supervised clustering analysis will be performed to provide a high-level view of the differences between the two groups analysed and to produce a differential gene expression (DEG) list. Enrichment analysis of the DEGs will be performed using the clusterProfiler software for enrichment analysis, including GO Enrichment, DO Enrichment, KEGG and Reactome database, to predict biological functions or pathways are significantly associated with DEGs. The top 5-10 genes from the DEG list will be validated by quantitative real-time PCR using RNA from mucosal tissue and also from PBMC and T cells isolated from peripheral blood. In addition, obtained biopsies will be defrosted and processed either by:

- 1. A whole tissue digestion protocol
- Placed in culture to allow crawl out of lymphocytes as previous described (Di Marco Barros Cell 2016)
- 3.

The resulting single cell suspension will either be analysed by flow cytometry (in the presence/absence of stimulation) or processed for transcriptomic analysis. Further, a single biopsy will be placed into RNAlater and subsequent RNA/DNA extraction performed. The resulting material will be saved for genotyping, gene expression analysis and T/B cell receptor analysis.

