1. Is there increased activation of STAT proteins in peripheral blood in patients who relapse?

The direct molecular targets of cytokine-induced JAK tyrosine kinases are the signal transducers and activators of transcription (STAT) proteins, which when phosphorylated become activated and translocate to the nucleus to bind DNA and induce cytokine specific gene expression and chromatin regulation⁵. STAT proteins are key molecular regulators of CD4-T-helper (Th) cell lineage differentiation programmes, which are directed and propagated following specific signature cytokine cues⁶. Aberrant activation of STATs is, thus, often a critical step in the molecular pathogenesis of several inflammatory and auto-immune diseases, that are associated with dysregulated Th function^{7,8}. Of the 7 STAT proteins, increased activation of STAT1, STAT3, and STAT5a/b in particular, and to a lesser extent STAT4 and STAT6, have been associated with the pathophysiology of UC, consistent with their activation by inflammatory cytokines involved in UC pathogenesis, such as IFNγ, IL12 (TH1), IL4, IL6, IL13, IL21 (TH2), IL6, IL23 (TH17), IL9 (TH9)⁹⁻¹³. Therefore, we will monitor the phosphorylation of STAT proteins in PBMC from patients enrolled in the study, with blood drawn before dose reduction.

2: Are there changes in cytokine expression in peripheral T cells that predict relapse?

The immunopathogenesis of IBD, including UC, is driven by the dysregulated expression of specific proinflammatory cytokines, secreted primarily by CD4 T-effector cells, which critically drives inflammation and tissue destruction¹⁴. These cytokines mediate their actions via STAT proteins, which are the subject of evaluation in question 1 above. To understand if there are changes in cytokine expression that predict relapse in specific patients, we will evaluate cytokine expression in peripheral CD4 T cells. The cytokines we will study are the key CD4 T-effector cytokines IFN γ , IL17, and IL9 corresponding to TH1, Th17 and Th9 lineages, that have been implicated in the pathogenesis of UC. These data will inform us of any changes in peripheral levels of pathogenic cytokines that predict patients who will relapse following tofacitinib dose reduction.

3: Can we identify signature gene(s) that serve as a biomarker to predict relapse?

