13.2 Data handling and record keeping

Pseudo-anonymised patient data will be kept on a password-locked computer. Every patient will be appointed a two-digit study number. All patient specific data will be recorded using only this number. The full name and birth date will only be recorded on the informed consent form. The study coordinator will monitor patient inclusion and protocol steps, coordinate data entry, perform data analyses and reporting. Data will be double entered into a Microsoft Excel spreadsheet to endure validity and quality.

All trial data will be stored in line with the Data Protection Act (1998). Records will be retained for a maximum of 7 years.

14 Statistical considerations

14.1 Sample size calculation (some pilot/feasibility studies may not require a formal sample size calculation)

Given the endpoints are exploratory, sample size calculations are not possible.

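### Section 10.3 measures secreted cytokines in supernatants from cultures in which secretion is deliberately blocked, so the supernatant ELISA is not interpretable as written

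*Protocol*

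**What the plan says.** Section 10.3 of the protocol describes the T-cell cytokine assay in consecutive sentences. The first sets the stimulation: "We will evaluate cytokine expression in peripheral CD4 T cells following PMA/ionomycin stimulation for 4hrs". It continues "in the presence of GolgiStop (to prevent cytokine secretion), followed by intracellular cytokine staining and FACS analysis", so the blocker is part of the culture and its purpose is given. The second sentence adds another read-out: "The supernatants from these cultures will be harvested and assessed for secreted cytokine expression", by ELISA specific for IL17, IFN-gamma and IL9. A third adds a test on plasma rather than on cultured cells: "Additionally, we will perform a multiplex cytokine array using the Th1/Th2/Th9/Th17/Th22/Treg ProcartaPlex Human Cytokine Array".

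Section 7.1 lists the measure among the biomarkers and outcome measures as "Cytokine expression in peripheral T cells". Question 2 of the Introduction (section 5) names IFN-gamma, IL17 and IL9 as the cytokines of interest and says of the CD4 T-cell evaluation: "These data will inform us of any changes in peripheral levels of pathogenic cytokines that predict patients who will relapse".

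**The concern.** An assay for secreted protein needs cultures that are free to secrete. Here the protocol takes the supernatant from cultures that contain a reagent added, in its own words, to stop secretion. If the laboratory follows the text, the three ELISA values per sample do not measure what they are labelled as measuring.

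Section 14.2 sends continuous variables to ROC-derived cut-offs, then to Kaplan-Meier comparisons by those cut-offs, and to univariate and multivariate models. Nothing there excludes the ELISA values. A lack of association with flare could mean that secretion does not predict flare, or only that secretion was blocked. An association could reflect differences in how completely the block worked, or in how the cultures were handled. The analysis could not tell these apart, and no later analysis plan can correct a supernatant collected under the blocker.

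**Working it through.** No arithmetic applies. The protocol gives no power or sample-size derivation (section 14.1: "Given the endpoints are exploratory, sample size calculations are not possible"), and the point does not depend on one. The check is a reading of section 10.3 against every other place where the cytokine measure appears.

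1. **Culture condition.** Section 10.3: PMA/ionomycin for 4 hours with GolgiStop present, whose stated role is to prevent secretion. No blocker-free interval within the stimulation is described.

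2. **Source of the ELISA sample.** Section 10.3, next sentence: the supernatants of the cultures just described. The only T-cell stimulation cultures described up to that point are those with GolgiStop.

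3. **Search for a way out.** A parallel culture without the blocker, or a harvest before the blocker is added, would remove the conflict. Neither appears in section 10.3. Sections 5, 7.1, 9.3, 10 and 13.1 name the cytokine measure or its timing but say nothing about culture conditions. Section 10.3 also describes biopsy cell suspensions analysed with or without stimulation, but those are mucosal cells and a different experiment.

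4. **What the ELISA would then measure.** If the blocker works as stated, cytokine is retained in the cells, and what reaches the supernatant is mainly release that escaped the block. The protocol does not say how complete the block is, so the size of the residual signal cannot be derived.

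5. **What is not affected.** Intracellular staining with FACS needs the cytokine kept inside the cell, so the blocker suits that read-out. It covers peripheral CD4 T cells, which is what sections 5 and 7.1 ask for. The multiplex array uses patient plasma, which is not exposed to the culture reagent.

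6. **Extent.** Three ELISA read-outs (IL17, IFN-gamma, IL9) in every blood sample processed this way. Baseline samples, which bear on prediction, number at most 50, one per enrolled patient. The number of later samples is not fixed: the section 7.2 flowchart marks research blood at both flare and week 44, section 10 says flare or week 44, and section 13.1 lists no cytokine item at flare.

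**The case against.** The strongest reply is that this is loose wording. Section 10.3 calls the methods standard and in routine use in the laboratory, and section 10.7 refers to an analytical plan agreed with the Chief Investigator, where well-level conditions could be set out. The second sentence might be meant to cover PMA/ionomycin stimulations in general. That is possible, but the text does not say it, and taken literally the text yields an invalid secretion read-out. A correction is needed under either reading.

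The reply is stronger on consequences. A reader might infer several things that the documents do not support:

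- *That three pre-named biomarkers are lost.* The listed biomarker is T-cell cytokine expression, and intracellular FACS still delivers it for the same three cytokines. No section lists supernatant cytokine as a separate biomarker or data item. The Introduction's sentence about peripheral levels refers to the CD4 T-cell evaluation as a whole, not specifically to the ELISA.
- *That the values will be near background in every patient, or unrelated to biology.* No blocking efficiency, assay sensitivity or expected level is given. Residual release might partly track production; the documents do not address this.
- *That about 100 samples are affected.* This assumes 50 baseline samples plus one follow-up sample per patient (50 + 50 = 100). The sampling passages do not settle on one follow-up sample.
- *That false positives would multiply.* Three read-outs add little to a candidate pool that already includes RNA sequencing, STAT phosphorylation and a multiplex array. Values with little spread would also leave little room for spurious association.

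These objections narrow the consequences. They do not remove the contradiction.

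**Conclusion.** Section 10.3 contradicts itself and is wrong as written: it blocks secretion in the cultures whose supernatant it then tests for secreted cytokine. The resulting values could not be read as the cells' secretory response, so no association with flare, null or positive, could be interpreted from them. The conclusion rests on the protocol's own statement of what GolgiStop is for, on the assumption that it works broadly as stated, and on the absence of any blocker-free culture in the text.

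The size is limited. One supplementary, exploratory read-out is compromised. The companion read-outs stand, so question 2 can still be answered from intracellular expression and plasma levels. The text should be corrected before samples are processed, but the point does not threaten the study's main objective.

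**What to change.** Amend section 10.3 to say which cultures supply the ELISA supernatants. Preferably, split each stimulated sample: one well with GolgiStop for intracellular staining and FACS, and a parallel well stimulated without GolgiStop whose supernatant goes to the IL17, IFN-gamma and IL9 ELISAs. If the laboratory already works this way, one added clause is enough.

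If cell numbers do not allow a second well, delete the supernatant ELISA and rely on intracellular staining and the plasma array already planned. That gives up the direct measure of stimulated T-cell secretion, which plasma levels do not replace.

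The parallel well uses blood already drawn and needs no extra patient procedure. Its cost is some additional cells per sample. The protocol gives neither blood volume nor cell yield, so whether there are enough cells is an assumption for the laboratory to confirm.
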